7.0 STATISTICAL ANALYSIS PLAN

7.1 Aim 1 Measures and Analyses

Data will be assessed for normality and transformations applied as needed (e.g., log). Neuropathic pain before and after acute cannabis administration will be assessed by NPRS and the von Frey test. Plasma AEA and 2-AG will be measured with LC/MS. Flow cytometry will quantify the percentage of PBMC that express CB2, FAAH, and MAGL, including monocytes, CD4+ T-cells, and CD8+ T-cells. To examine the effect of different CBD/THC products on NP and EC biomarkers, we will use a linear mixed model with subjects treated as a random effect to model the response measures. This methodology takes into account the repeated measures aspect of the within-subjects crossover study design, incorporating information from observations for each subject at different treatment doses and multiple time points within each dose. For initial modeling, terms will include dose (0.01%, 5.1% - 4 puffs, and 5.1% - 8 puffs) CBD treated as a categorical variable), time (0, 60, 120 and 180 minutes after exposure treated as a continuous variable), and dose x time interaction. Additional terms will also be included for the sequence in which the treatments were administered (e.g., low CBD vs. medium CBD) and for second-order time (time²). The quadratic term is intended to model a U-shaped response curve if responses initially increase (or decrease), reach a maximum (or minimum), then decrease (or increase) back to baseline levels. For each outcome measure, each of these last 2 terms will be omitted from subsequent models and not reported if nonsignificant. Any potential factors that associate with outcome variables at the $\alpha = 0.20$ level in single-predictor analyses (history of light vs. heavy cannabis use, mode of prior cannabis use – i.e., engaging in smoking, or vaporizing, or both), time since last cannabis use before baseline, duration of cannabis use over lifetime, presence of adolescent cannabis use, duration of HIV infection, nadir CD4, viral load, gender, the presence of other non-cannabis analgesic medications, history of non-cannabis substance use disorders) will be included in the linear model. Dose effects at each time point will be assessed with mixed modeling after re-coding time as a categorical factor and including dose and dose x time terms (plus a term for sequence if this is significant in the initial model). Differences among doses will be evaluated using the Tukey honestly significant difference (HSD) comparison tests for differences of effects over all time points and contrasts within each

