
time point. All response observations, including information from subjects who do not complete all experimental sessions, will be included in the analyses. Similar mixed-model analyses will be performed on the primary pain outcome after adjustment for psychomimetic side effects (measured with the ARCI scale) to assess for effects of the study drug on pain independent of subjective responses. The proportion of subjects with a 30% pain reduction, a standard for effective pain reduction⁶⁰ will be compared between each of the doses with chi-square tests; we will also calculate the number needed to treat (NNT) for a 30% pain reduction rate. We will also conduct analyses to examine the association between pain and EC biomarkers, including AEA, 2-AG, FAAH, and MAGL expression. A 5% significance level will be used for all testing. The association of pain levels with HRV will use a linear mixed-effects model, adjusting for potential confounders as above. Within-subject correlation will be accounted for using subject-specific random intercepts and slopes.

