7.2 Aim 2 Measures and Analyses

Based on our existing data for PLWH SMS compliance, we anticipate that participants will respond to 80-90% of the daily text messages during IMPACT. To address the issue of missing data, we will incorporate questions that allow participants to indicate their pain and cannabis use for the prior day if they did not respond to the earlier message. For days that have completely missing data, we will treat the intermittently missing data as missing completely at random. However, this assumption will be checked in sensitivity analyses by comparing the outcomes of participants based on the amount of missing data. Study dropout will be examined separately using statistical methods in current use [Diggle, Heagerty, Liang, and Zeger, *Analysis of Longitudinal Data*, 2nd ed., Oxford University Press, 2013]: The relationship between CBD, THC, and the CBD/THC ratio during a cannabis exposure event to changes in pain before and after the event will be examined using longitudinal data methods – e.g., mixed-effects linear models, controlling for potential confounders including baseline pain, in addition to those listed under Aim 1. The total CBD and THC consumed during the exposure will be calculated using the SUI method, estimating total grams of cannabis consumed multiplied by the percentages of CBD and THC content. Subject-specific random intercepts will be included in the model in order to account for the within-subject correlation of the outcome. Exploratory analyses will examine if there are different effects of reported cannabis strain (Sativa, Indica), individual types (e.g., OG Kush, Sour Lemon, etc.), or mode (smoking, vaporizing, ingesting food product) on pre-post changes in NP. We will also conduct exploratory analyses to examine if there is an interaction between reported levels of THC (low, < 1%, medium, 1-6%, high, > 10%) and CBD (low, < 1%, medium, 1-6%, high, > 10%) on pain change after drug use. The association of daily measures of pain levels with HRV will use a linear mixed-effects model, adjusting for potential confounders. The within-subject correlation will be accounted for using subject-specific random intercepts. Longitudinal changes in HRV between the first and last week will be assessed with a linear model that includes cannabis use (light vs. heavy) and CBD/THC intake, as predictors. Regression analyses will also examine the association between HRV and self-report pain measures quantified at the baseline and final visits.

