7.3 Aim 3 Measures and Analyses

We will use a linear model to examine the association between the total CBD, THC, and CBD/THC ratio during IMPACT and the change in NP, disease markers (CD4, viral load, Total Neuropathy Score, and neurocognitive global T-score), and EC biomarkers (AEA, 2-AG, FAAH, MAGL, CB2) from baseline to the final visit after month 6. We will control for confounders as in Aims 1 and 2, including any CBD and THC levels recorded at the baseline and final sessions. Linear models will compare the month 6 – baseline change in pain and in EC biomarkers between the heavy- and light-cannabis groups. One exploratory analysis will test for an interaction between group (light vs. heavy) and CBD and THC levels on change in NP and EC biomarkers. We will assess if exposure mode (smoking/vaporizing/ingestion) predicts pain outcome. We will examine if there is an association between pain change over time and changes in EC biomarkers. During the 6-month IMPACT, alterations may occur in cannabis use or pain medication (e.g., a person enrolled as a light cannabis user may start to engage in heavy use or begin using non-cannabis medication for pain, i.e., an opiate, which we will record with IMPACT). To address these issues we will conduct light vs. heavy use analyses based both on the baseline group classification and the actual use during IMPACT, include a cannabis use 'change' factor in the analyses (going from light to heavy use, or vice versa), and include the initiation of any non-cannabis pain medication as a factor in the model.

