For Aim 2, with 20% attrition over the 6 months of IMPACT we have $n= 80$ participants with 6 months (26 weeks) of data. We conservatively ignore the drop-out participants (who nonetheless contribute partial data). Assume, conservatively, that participants will use cannabis on average 2 times/week. This gives $n=80$ and $k=52$ observations/participant. If ICC is the intra-class, or within-participant correlation, the effective sample size (number of equivalent independent observations) is $n_{\text{eff}} = n/(ICC+(1-ICC)/k) \approx n/ICC$ [e.g., Killip, Mahfoud, Pearce, Ann Fam Med, 2004; 2:204-208.]. Assuming conservatively $\rho=0.5$ (or lower), we get $n_{\text{eff}} = 2n = 200$ [$n_{\text{eff}} = 160$]. We have 80% power to detect a (partial) correlation R between the individual predictors (Hypothesis 1: CBD, THC, and the CBD/THC ratio; Hypothesis 2: pain levels and HRV) and change in pain of $R = 0.218$ (or semi-partial $R^2 = 0.0475$), after adjusting for confounders. Calculations used G*Power.

For Aim 3, assuming $n = 80$ participants complete the 6-month follow-up, we have 80% power to detect an association between an individual predictor and response (e.g., total CBD and changes in neuropathic pain levels) of $R = 0.302$ (or semi-partial $R^2 = 0.092$), after adjusting for confounders. The calculations used G*Power.

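### Age is missing from the covariate list that the HRV–pain and Aim 3 models rely on, and the baseline/final-visit HRV–pain regression names no covariates at all

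*Combined protocol and SAP*

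**What the plan says.** Section 7.1 lists eleven candidate factors. Five describe cannabis history: light or heavy use, mode, time since last use, lifetime duration and adolescent use. The other six are "duration of HIV infection, nadir CD4, viral load, gender, the presence of other non-cannabis analgesic medications" and history of other substance use disorders. A factor enters a model only if it is associated with the outcome at the 0.20 level in a single-predictor analysis. Neither age nor antiretroviral treatment is listed.

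Later adjustment sets build on this list:

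- **Aim 1 HRV–pain mixed model (7.1):** the same confounders as the dose model.
- **Aim 2 model of cannabinoids and pain change (7.2):** the Aim 1 list plus baseline pain.
- **Aim 2 daily HRV–pain model (7.2):** unspecified potential confounders.
- **Aim 2 visit-level regression (7.2):** "Regression analyses will also examine the association between HRV and self-report pain measures quantified at the baseline and final visits". No covariates are named.
- **Aim 3 (7.3):** "We will control for confounders as in Aims 1 and 2". It adds measured CBD and THC levels, a factor for change in use group, and the start of a non-cannabis pain drug. Its outcomes include changes in CD4 and viral load.

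Age is an eligibility item (3.1.2: adults, no upper limit). Section 5.3 says HIV treatment is left unaltered; no section says that antiretroviral status or adherence is recorded.

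**The concern.** The plan proposes HRV as an objective biological measure of pain. Its relationship with pain is among the primary outcome measures in Section 2.0 and is a powered hypothesis in 7.4. With an adult sample of unrestricted age, HRV and pain may both vary with age. If they do, older and younger participants will differ on both, and a between-person regression will show an HRV–pain association even where HRV carries no information about pain. The visit-level regression is the most exposed, because it compares people and states no adjustment. The mixed models also use within-person variation, but they do not separate it from the between-person part, so age can still enter.

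Aim 3 is less exposed. Its outcomes are six-month changes, so age biases them only if it is related both to cannabinoid intake and to the change. For CD4 and viral load, the parallel worry is antiretroviral treatment, which neither the entry criteria nor the adjustment list addresses.

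**Working it through.** **Inputs from the documents.** "A 5% significance level will be used for all testing" (7.1); I take this as two-sided. n = 100 at baseline and n = 80 after 20% attrition (7.4). Aim 2, which contains the HRV–pain hypothesis: "change in pain of $R = 0.218$ (or semi-partial $R^2 = 0.0475$), after adjusting for confounders". Aim 3: "For Aim 3, assuming $n = 80$ participants complete the 6-month follow-up, we have 80% power to detect an association" "of $R = 0.302$ (or semi-partial $R^2 = 0.092$), after adjusting for confounders".

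**1. The plan's own figures reproduce.** For one regression coefficient, f² = R²/(1 − R²), noncentrality = √(n·f²), df = n − p − 1, where p is the number of model terms.

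- Aim 3: R² = 0.302² = 0.0912; f² = 0.0912/0.9088 = 0.1004; noncentrality = √(80 × 0.1004) = 2.83; power 0.799 with p = 1.
- Aim 2: R² = 0.218² = 0.0475; f² = 0.0475/0.9525 = 0.0499; noncentrality = √(160 × 0.0499) = 2.83; power 0.802. Section 7.4 prints both 200 and 160 as the effective sample size; 200 would give 0.882, so the stated R rests on 160.

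**2. Spurious correlation if age is omitted.** In a standardised linear model with no true HRV–pain link, |r(HRV, pain)| = |r(age, HRV)| × |r(age, pain)|. The documents give neither correlation, so both are assumed: 0.3–0.5 with HRV and 0.1–0.3 with pain. The rejection rate is by Fisher z: Φ(atanh(r)·√(n − 3) − 1.96), plus the small opposite tail.

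| Assumed correlations | Spurious r | Rejection, n = 80 | Rejection, n = 100 |
|---|---|---|---|
| 0.3 × 0.1 | 0.03 | 6% | 6% |
| 0.4 × 0.2 | 0.08 | 11% | 12% |
| 0.5 × 0.3 | 0.15 | 26% | 32% |

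For the last row at n = 100: atanh(0.15) = 0.151; × √97 = 1.49; 1.49 − 1.96 = −0.47; Φ = 0.32. The noncentral t method of step 1 agrees (27% and 32% for r = 0.15).

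The right comparator is the Aim 2 detectable R of 0.218, since 7.4 places pain and HRV under Aim 2: 0.15/0.218 = 0.69, so the upper end is about two thirds of it.

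**3. Why listing age would not be enough.** Under the 0.20 screen, a factor correlated 0.1 with the outcome enters with probability 0.36 (n = 80) or 0.40 (n = 100); at 0.2, 0.70 or 0.77; at 0.3, 0.94 or 0.97. Across the assumed age–pain range, entry is far from assured.

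**4. Cost of adjustment.** Start from p = 12 (eleven listed factors plus the predictor, one degree of freedom each) and add both age and antiretroviral status, p = 14. Aim 3 power at R = 0.302 stays at 0.797 and detectable R moves from 0.3029 to 0.3030. Aim 2 power at 160 stays at 0.801 to 0.802. These figures take R as the association remaining after adjustment, as 7.4 does.

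**The case against.** The strongest reply is that the omission is a risk and not a demonstrated bias. Most of this stands.

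- A reader might infer that the HRV–pain and Aim 3 results will be confounded. The documents do not show that: they contain no correlation of age with HRV, pain, intake or change, and the lower end of the illustration is close to the nominal 5%.
- A reader might take the covariate list as closed. It is not strictly so: 7.2 speaks of potential confounders in general terms, and 7.3 adds several factors. A covariate that is never named is still not pre-specified.
- Durations of HIV infection and of cannabis use partly carry age, and the illustration gives them no credit. They are incomplete stand-ins, must pass the 0.20 screen, and are not named for the visit-level regression.
- In that regression age is unadjusted because no adjustment set is given. Adding age to the 7.1 list would not by itself repair it. The text also does not say whether the two visits are analysed separately, pooled or as change; the between-person reading is the natural one for separate or pooled analysis, but it is an inference.
- A reader might infer that antiretroviral status can be read from trial records just as age can. The documents support this for age only. No magnitude can be given for the antiretroviral part, and a baseline value would not capture changes during follow-up. That part is therefore conditional.

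**Conclusion.** The concern holds as a gap in pre-specification. Followed as written, the plan leaves between-person HRV–pain associations, and to a lesser degree the Aim 3 change models, without a named adjustment for age. The possible effect runs from negligible to material: spurious r of 0.03–0.15 and false-positive rates of about 6–32%, resting wholly on assumed correlations, a linear model, no true HRV–pain link and no credit for partial proxies.

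Two further inferences would go too far. The randomised within-person dose comparison is not threatened, because each participant serves as their own control and age does not differ between doses. No stated detectable effect or power figure is wrong on this account; the 200 versus 160 effective sample size in 7.4 is a separate matter.

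**What to change.** In the SAP text:

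1. Include age as a forced covariate, exempt from the 0.20 screen, in the Aim 1 and Aim 2 pain–HRV models and in the Aim 3 models.
2. State the covariates for the baseline/final-visit HRV–pain regression in 7.2, with age explicitly among them.
3. State whether antiretroviral status is recorded. If it is, include its baseline value in the CD4 and viral-load change models, and acknowledge that this does not address treatment changes during follow-up.

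The cost is a wording change and one or two degrees of freedom, with no visible change in power. Age needs no new data collection. Antiretroviral status needs none if it is already recorded.

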HIV-associated neuropathic pain (HIV-NP) affects a significant proportion of people living with HIV (PLWH) and has a major impact on everyday functioning and quality of life in this population. Over the past decade a growing number of preclinical studies and clinical trials have indicated that cannabis administration and manipulation of the endocannabinoid (EC) system may have therapeutic utility in addressing HIV-NP. EC CB2 receptor activation and inhibition of the EC deactivation enzymes fatty acid amide hydrolase (FAAH) and monoacylglycerol lipase (MAGL) have been shown to decrease pain in rodent models of HIV-NP, while acute exposure to cannabis reduces self-reported pain in PLWH with neuropathy. However, little work has been conducted to elucidate the effects of the two primary cannabinoids (delta-9-tetrahydrocannabinol, THC and cannabidiol, CBD) on the EC system or to assess EC function in PLWH. The objective of this application is to address these fundamental gaps in our knowledge by: 1) examining the acute effect of administering NIDA-prepared THC/CBD products on HIV-NP; 2) utilizing mHealth text messaging to monitor daily real-world self-administered cannabis effects on pain; 3) assessing the relationship between cannabinoids and EC biomarkers, including ligands, enzymes, and receptor expression; and 4) conducting exploratory analyses to evaluate the effect of longitudinal cannabinoid use on changes in HIV-NP over time. We will examine the effect of low (0.01%), medium (one vial of 5.1%), and high dose (two vials of 5.1%) CBD-containing cannabis on NP, the EC system, and heart rate variability (as a proposed objective biological measure of pain) in 100 PLWH who use cannabis to treat neuropathic pain. We will subsequently employ a mobile phone text messaging system, the Individual Monitoring of Pain And Cannabis Taken (IMPACT), to track cannabis exposure, CBD and THC consumption, and pain over a period of 6 months in these same PLWH participants. IMPACT will be used to quantify the real-time effects of acute CBD/THC exposure on pain before and after cannabis self-administration, the real-time relationship between self-reported pain and changes in HRV, and to assess any longitudinal changes in NP, HIV clinical outcomes (viral load, CD4) and cognition during the 6-month period. This plan allows us to acquire data and compare the effects of cannabis product obtained from NIDA and self-administered cannabis obtained from local medicinal dispensaries. The overarching hypothesis is that CBD exposure and a higher CBD/THC ratio will exert beneficial effects both in the laboratory and during the observational study, including increasing EC biomarkers and reducing NP. In summary, this approach will advance our understanding about several key issues, including the interaction between cannabis constituents, the EC system and pain, the biological mechanisms that underlie these effects (EC enzymes, receptor), and the longer-term effects of cannabis use on health-related outcomes in HIV, including predictors of mortality (HRV, CD4, viral load) and neurocognition.

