7.4 Power Analyses

A recent study indicated a medium effect size (Cohen's $d = 0.46$) for CBD treatment that increased plasma AEA levels compared to an antipsychotic drug control condition²⁶. Preclinical models of neuropathic pain in mice demonstrate that FAAH inhibitors decrease hyperalgesia

and allodynia with large effect sizes (Cohen's $d = 4-5$)¹⁸. Our pilot HRV data indicate a medium to large effect size (Cohen's $d = 0.8$) for reduced RMSSD in PLWH with neuropathic pain compared to PLWH without neuropathy. We conducted power calculations with the G*POWER software⁹² comparing the area under the curve (AUC) of the change from baseline in pain levels between the three doses of cannabis. The actual analyses will have higher power, since they rely on a longitudinal mixed-effects model. With $n=100$ participants completing the cross-sectional baseline visits, and measured in a within-participant design, as described above, we have 80% power to detect an effect size Cohen's $f=0.180$. This Cohen's f corresponds to a range of group means for the three groups corresponding to a small-to-medium Cohen's $d = 0.382-0.441$. We have 0.61-0.76 power to detect such a pairwise difference as statistically significant in post-hoc analyses (e.g., with Bonferroni correction for post-hoc comparisons). If the completion rate at this stage is 95% (90%) of the initial enrollment of $n=100$, the detectable effect size is Cohen's $f=0.185$ (0.190). These correspond to a range of group means for the three groups corresponding to small-medium Cohen's $d = 0.403-0.465$.

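### Aim 1 tests dose on pain in an overall Tukey comparison, again at each of four times, and through dose x time, with no ranking or error control across them

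*Combined protocol and SAP*

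**What the plan says.** Section 7.1 fits a mixed model with "dose (0.01%, 5.1% - 4 puffs, and 5.1% - 8 puffs) CBD treated as a categorical variable" and "time (0, 60, 120 and 180 minutes after exposure treated as a continuous variable), and dose x time interaction". A second model follows: "Dose effects at each time point will be assessed with mixed modeling after re-coding time as a categorical factor". Differences among doses are then judged with "Tukey honestly significant difference (HSD) comparison tests for differences of effects over all time points and contrasts within each" time point. With three doses, that is three pairs overall and three pairs at each of 0, 60, 120 and 180 minutes, so 3 + 12 = 15 pairs. The proportions with a 30% pain reduction "will be compared between each of the doses with chi-square tests", with no adjustment named. On the error rate the section says: "A 5% significance level will be used for all testing".

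Section 7.1 mentions a primary pain outcome once and attaches no time point or dose pair to it. Section 2.0 lists the acute effect on pain among the primary outcome measures, also without a contrast. Section 7.4 bases its power calculation on "comparing the area under the curve (AUC) of the change from baseline in pain levels between the three doses of cannabis", adds that the actual analysis is a longitudinal mixed model, and describes the pairwise tests as post-hoc, with Bonferroni as an example. The opening summary states a direction: "The overarching hypothesis is that CBD exposure and a higher CBD/THC ratio will exert beneficial effects".

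**The concern.** The point concerns the tests within one outcome, the pain score, and not the number of outcomes. Tukey protects the three dose pairs inside one family. It does nothing across the overall family, the four time-point families and the dose x time test. Because these are unranked, any one of 15 pairs or the interaction could be reported as an effect of dose on pain. The results can also disagree: high and low CBD may not differ overall but differ at 120 minutes, and the plan does not say which finding prevails. At stake are the false-positive rate of the trial's main randomised question and some power. A contrast that matches the stated hypothesis pays a multiplicity price that it would not pay if named in advance.

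**Working it through.** **Inputs from the documents.** Three doses, four post-dose times, 5% per test and Tukey HSD (7.1). n = 100 within-participant, 80% power, f = 0.180, d = 0.382-0.441, pairwise power 0.61-0.76 (7.4).

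**Assumed.** The correlation between the four pain scores within a session is not given, so it is varied from 0 to 0.9. The variance model is taken as correctly specified.

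**Step 1: reproduce the plan's power.** With zero correlation between doses within a person, the noncentrality is f² × n × 3 = 0.0324 × 300 = 9.72. The three-dose F test then has power 0.797 (2 and 198 df) or 0.799 (2 and 297 df), against 0.80 stated. The d range is 0.180 × 6/√8 = 0.382 to 0.180 × √6 = 0.441. For one pair the noncentrality is d × √(n/2), giving 0.382 × 7.071 = 2.70 and 0.441 × 7.071 = 3.12. At alpha 0.05/3 and 198 df the power is 0.613 and 0.759. The plan's figures reproduce.

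**Step 2: false dose claims when doses do not differ.** There were 100,000 simulated trials per setting, with n = 100, 3 doses and 4 times. Tukey used the studentized range critical value 3.34 (3 groups, 198 df), applied at each time and to the mean over times. Dose x linear time used a 2-df F test at 5%. Results for equal correlation between times:

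| Within-session correlation | Overall Tukey family only | Five Tukey families | Five families plus dose x time |
|---|---|---|---|
| 0 | 4.7% | 19.7% | 21.6% |
| 0.3 | 4.8% | 17.7% | 20.2% |
| 0.5 | 4.8% | 15.6% | 18.8% |
| 0.7 | 4.8% | 13.0% | 16.6% |
| 0.9 | 4.7% | 9.2% | 13.4% |

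A correlation that decays with time separation gives similar values (10.2-19.8% and 13.9-21.7%). If the tests were independent, the ceilings would be 1 − 0.95⁵ = 22.6% and 1 − 0.95⁶ = 26.5%.

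**Step 3: other readings of the Tukey sentence.**
- One Tukey family over all 12 dose-by-time cells, plus the overall family: 4.7-5.6%, or 9.2-9.9% with dose x time.
- Time-point contrasts only after a significant dose x time test: about 9%.
- No Tukey correction within time points: about 21-41%.

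**Step 4: power of one named contrast.** Using the noncentralities in step 1:

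| Rule | d = 0.382 | d = 0.441 |
|---|---|---|
| One contrast, two-sided 5% (99 df) | 0.763 | 0.870 |
| Bonferroni over three pairs (99 df) | 0.606 | 0.751 |
| Bonferroni over three pairs (198 df) | 0.613 | 0.759 |

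**Not counted.** The responder tests, the von Frey test and the model adjusted for subjective drug effects are left out. Three unadjusted paired responder comparisons would have a familywise error of about 12%. The unpaired chi-square would give less if responses are positively correlated within a person.

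**The case against.** The strongest reply is that the plan already contains a multiplicity-adjusted dose comparison over all times, and that this family holds about 5%. That stands: a reader might infer that Aim 1 has no controlled dose comparison at all, and the documents do not support it. The plan has one but does not label it decisive.

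A reader might also infer that the plan breaks a promised 5% familywise rate. It promises 5% per test and no familywise rate, so the defect is missing control and not a broken promise. Nor is any single inflated percentage a fact about the plan: the Tukey family is not defined, the within-session correlation is assumed, and the higher range counts dose x time as a dose claim.

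It is tempting to treat the AUC comparison in 7.4 as a rival primary analysis. That section uses it to approximate power and says that the mixed model is the real analysis. Its post-hoc wording suggests an overall test before the pairs, but neither section makes this a rule, and it would not cover the time-point families.

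Finally, an all-pairs comparison is defensible, since section 1.1 says the best THC/CBD ratio is unknown. Section 7.2 also singles out 60 and 120 minutes when comparing laboratory and dispensary cannabis. These are reasons to debate which comparison should decide, not to leave it open.

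**Conclusion.** The concern holds in this form: section 7.1 neither ranks the overall, time-point and dose x time tests on pain nor controls error across them. On the natural reading, the chance of at least one false dose claim is about 9-20% from the five Tukey families and about 13-22% with dose x time. It would be near 5% (9-10% with dose x time) under a single 12-cell family that the plan does not state. The figures rest on the assumed correlation range and on session-level correlation being modelled. Section 7.1 names only a subject random effect for the dose model, and ignoring session correlation would raise the error further. The data stay usable whatever is chosen, so this should be settled before analysis but does not threaten the trial.

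**What to change.** In 7.1, state that the overall dose comparison on the NPRS across the post-dose times alone decides Aim 1 on pain. Include the pre-dose score as a covariate, or analyse change from baseline to match 7.4.

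Preferably make this one contrast, the high versus low CBD product at two-sided 5%. It matches the directional hypothesis and, at the plan's own effects, has power of about 0.76/0.87 against 0.61/0.75-0.76 with Bonferroni. Test the other two overall pairs, keeping Tukey, only if it is significant. THC also differs between the products (1.9% and 1.4%), so describe the contrast as comparing products and not CBD alone. Section 7.1 labels doses by puffs, 4.1 by vials, and 4.2 gives both 4 and 8 puffs. These passages must be reconciled so that the contrast is unambiguous.

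Report dose x time and the 12 within-time contrasts as estimates with intervals, or adjust them jointly over dose and time. Compare responder pairs only after an overall three-dose test.

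The cost is a few sentences in 7.1 and a matching line in 7.4, with no extra participants or data. The downside is that an effect at one time point only, or a peak at the medium dose, becomes a secondary result.
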